## **BACKGROUND**

To develop a viable and sustainable best practice model to promote elderly mental wellness and prevent elderly depression for Hong Kong, the Hong Kong Jockey Club Charities Trust has initiated a pilot holistic support project entitled “JC JoyAge: Holistic Support Project for Elderly Mental Wellness”. This project aims to develop and implement a collaborative stepped care and peer support programme for effective outreach, engagement, and prevention of depression among older people in four pilot districts in Hong Kong, namely Kwun Tong, Sham Shui Po, Kwai Chung, and Tseung Kwan O.

## **Objectives**

1. To evaluate the effectiveness of a collaborative stepped care and peer support programme in engaging older people at-risk of or with depression.
2. To evaluate the efficacy of the programme in reducing symptoms/risks and promoting wellbeing in older people at-risk of or with depression.
3. To investigate the impact of the programme on care resources utilization in these older adults.

## **Methods**

### Design

This study adopts quasi-experimental design and compares older adults at-risk of or with depression receiving the stepped collaborative care (intervention group) versus those receiving standard care (control group).

### Participants

1. Intervention Group: older people at-risk of having depression (n=1,600) and those with clinically significant depressive symptoms (n=400) recruited from NGOs providing the intervention in four pilot districts in Hong Kong
2. Control Group: older people at-risk of having depression (n=400) and those with clinically significant depressive symptoms (n=100) referred by different NGOs in Hong Kong and recruited through open recruitment

The inclusion criteria are:

- age 60 years or above; and
- residing in Kwun Tong, Kwai Chung, Tseung Kwan O, or Sham Shui Po; and
- have one or more known risk factor(s) for developing depression; and/or
- have depressive symptoms of mild level or above; and
- able to give informed consent to participate

The exclusion criteria are:

- known history of autism, intellectual disability, schizophrenia-spectrum disorder,
- bipolar disorder, Parkinson's disease, or dementia
- (temporary exclusion criteria) imminent suicidal risk;
- and difficulty in communication

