#### Interventions

The intervention group will receive a collaborative stepped care programme provided by registered social workers and trained peer supporters from elderly or mental health service units (NGOs) according to level of risks, symptom severity, and intervention response. Home visits or other format of contact will be delivered by trained peer supporters employed by NGOs to detect and engage hidden cases.

For “at-risk” group, 4 weeks of “selective prevention” group sessions will be provided at the elderly service level by trained peer supporters with registered social worker supervision, on wellness topics tailored to the person’s concern as entry point, packaged with mental health information, followed by a review. If the review shows no significant improvement, a further 2-4 weeks of group plus individual casework sessions will be provided.

For people with depressive symptoms, we further divide them to “mild” and “moderate” groups. For mild group, 6-8 weeks of indicated prevention with psychoeducation or low-intensity psychotherapy would be provided. For moderate group, 6-8 weeks high- intensity cognitive behavioral therapy (CBT) would be provided. All intervention for depressed elderly would be conducted by registered social workers who are trained by this project and employed by the NGOs. The trained peer supporters will be matched to individual older adults to walk them through the process.

The control group will receive treatment as usual, which will be determined by the responsible worker from NGO units.

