### Data Analysis

We will generate descriptive statistics of the demographic and clinical variables at the baseline (T0/Intake) assessment. The independent sample t-test will be used to compare the means of continuous variables in the intervention and control groups; the chi-square test will be used to compare categorical variables; and Fisher exact test will be used for variables with low cell counts ( $n < 5$ ). For the majority of clinical scales that are ordinal in nature, the independent samples Mann-Whitney U-test will be used to examine whether the same distributions could

be assumed across groups. As observations at two /three time points are nested within individuals and individuals are nested within clusters (centers), changes in outcome measures, including PHQ-9 and GAD-7 scores, will be assessed by a three-level linear mixed model. Because the number of clusters is small, degree-of-freedom correction using the Satterthwaite method will be applied to the mixed models to maintain the desired type I error rate (Leyrat, Morgan, Leurent, & Kahan, 2017). We will use STATA 14.1 (StataCorp, 2015) for data analysis. For all the tests, the statistical significance level was set at .05.

To investigate engagement in the intervention versus control group, the following analyses will be conducted: (1) Cox proportional hazard regression analysis of the time to the primary endpoint of voluntary withdrawal from service; (2) Chi-square test of initial refusal of service by eligible participants after screening.

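### Recruitment is split into at-risk and symptomatic strata, but no stratum adjustment or stratum-specific estimate is planned for PHQ-9 and GAD-7 (cheap improvement)

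*Combined protocol and SAP*

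**What the plan says.** **Targets.** Participants sets the intervention arm at "older people at-risk of having depression (n=1,600) and those with clinically significant depressive symptoms (n=400" and the control arm at "older people at-risk of having depression (n=400) and those with clinically significant depressive symptoms (n=100". Intervention participants come from the NGOs that deliver the programme. Controls are referred by different NGOs or come through open recruitment. The Design section states: "This study adopts quasi-experimental design and compares older adults at-risk of or with depression".

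**Components.** Under Interventions, at-risk people in the intervention arm start with 4 weeks in which "group sessions will be provided at the elderly service level by trained peer supporters with registered social worker supervision". People with symptoms are divided into mild and moderate and receive 6-8 weeks from social workers. Controls receive treatment as usual, with no components tied to stratum.

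**Analysis.** Data Analysis says that "changes in outcome measures, including PHQ-9 and GAD-7 scores, will be assessed by a three-level linear mixed model". The levels are time points, individuals and centres. No fixed effects are listed. It adds: "Because the number of clusters is small, degree-of-freedom correction using the Satterthwaite method will be applied to the mixed models". Baseline comparability is handled descriptively and by tests between groups: "We will generate descriptive statistics of the demographic and clinical variables at the baseline (T0/Intake) assessment".

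**Aim.** Objective 2 is "To evaluate the efficacy of the programme in reducing symptoms/risks and promoting wellbeing in older people at-risk of or with depression", which names both strata together.

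**The concern.** The plan treats the two strata differently in recruitment, assessment length and (in the intervention arm) treatment, but the outcome analysis does not mention them. Two things follow.

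- **Interpretation.** A single estimate is weighted about 80:20 towards at-risk people. A modest overall effect could come entirely from the social-worker tier or entirely from the peer-supporter tier, and the planned result could not tell these apart. The Background says that the project is meant to develop a best-practice model, so the distinction is useful.
- **Protection.** The arms are not randomised and are recruited by different routes. Symptomatic people may improve more whatever they receive, through natural change and regression to the mean. If one arm ends up with a larger symptomatic share, part of the group difference in change reflects who was recruited. The baseline tests could reveal such a gap but would not adjust for it.

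**Working it through.** **Inputs from the documents.** Targets are 1,600/400 and 400/100; alpha is .05 (two-sided assumed). T0 and T2 are the only assessments common to both arms. The documents give no SD, effect size, intracluster correlation or dropout rate, so there is no stated power figure to reproduce.

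**Inputs assumed.** SD of PHQ-9 change 2.5 (at-risk) and 5 (symptomatic); an extra natural fall f of 2 points in symptomatic people in both arms (range 1-3); no true effect unless stated; no dropout; design effect 1, then 2.

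**1. Weights.** 1,600/2,000 = 400/500 = 80%, and 400/2,000 = 100/500 = 20%. Overall effect = 0.8 x at-risk + 0.2 x symptomatic. A value of 0.4 points arises from effects of 0 and 2 (0.2 x 2), or of 0.5 and 0 (0.8 x 0.5).

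**2. Gap in mix.** Let the symptomatic share be 20% + g in the intervention arm and 20% in control.
- Bias = g x f.
- v(p) = (1-p) x 6.25 + p x 25 + p(1-p) x f².
- SE = sqrt(v(0.2+g)/2000 + v(0.2)/500), multiplied by sqrt(2) for a design effect of 2.
- At f = 2: v(0.20) = 10.64, v(0.25) = 11.69, v(0.30) = 12.72.

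| Gap g | Bias (f = 2) | SE | False positives | Range, f = 1-3 | Design effect 2 (f = 2) |
|---|---|---|---|---|---|
| 0 | 0 | 0.163 | 5% | 5% | 5% |
| 5 points | 0.1 | 0.165 | 9.3% | 6.1%-14.2% | 7.1% |
| 10 points | 0.2 | 0.166 | 22.5% | 9.4%-41.3% | 13.6% |

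Simulation with the stratum counts held fixed gave 7.6% and 18.9% for the two gaps without clustering, with the same biases.

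**3. Effect of adjusting.** With stratum and stratum x time in the model, arms are compared within stratum, so a gap in mix no longer produces this bias. At the planned targets the SE is sqrt(0.8 x 6.25 + 0.2 x 25) x sqrt(1/2000 + 1/500) = 3.162 x 0.05 = 0.158, against 0.163 without the term. In a common-variance model each stratum is weighted by n1 x n0/(n1 + n0). This is 1600 x 400/2000 = 320 and 400 x 100/500 = 80, or 80:20. At a 10-point gap it is 1400 x 400/1800 = 311 and 600 x 100/700 = 86, or about 78:22. The overall estimate keeps essentially the same meaning.

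**4. What stratum estimates can detect (80% power).** Detectable difference in SD units = 2.80 x sqrt(1/n1 + 1/n0).

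| Contrast | Design effect 1 | Design effect 2 |
|---|---|---|
| Overall, 2,000 v 500 | 0.14 | 0.20 |
| At-risk, 1,600 v 400 | 0.16 | 0.22 |
| Symptomatic, 400 v 100 | 0.31 | 0.44 |

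For the difference between the stratum effects, the stratum SEs are 2.5 x sqrt(1/1600 + 1/400) = 0.140 and 5 x sqrt(1/400 + 1/100) = 0.559. The combined SE is sqrt(0.140² + 0.559²) = 0.576, so about 2.80 x 0.576 = 1.6 points is detectable, or 2.3 at a design effect of 2.

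**5. Masking.** With a 2-point symptomatic effect and at-risk effects of 0, 0.1 and 0.2, the overall effect is 0.40, 0.48 and 0.56. Power at SE 0.158 is 72%, 86% and 94%, against 95% in the symptomatic stratum alone (before clustering).

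**The case against.** The strongest case against is that nothing here contradicts a stated aim. Objective 2 concerns the programme as a whole, a pooled estimate can answer it, and equal 80/20 targets act as quotas that limit imbalance. Nothing in the documents suggests that a 5- or 10-point gap will occur. All of this stands, and it is why the point is an improvement and not an error.

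Three stronger readings are tempting, and the documents do not support them.
- *The plan excludes stratum.* Data Analysis lists no fixed effects at all, not even group or time. It is silent and records no decision.
- *Both arms receive stratum-specific components.* Only the intervention arm does.
- *The planned result will be biased, or will hide a real effect.* The bias needs a realised gap in mix, and step 5 shows that masking is narrow.

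It is also fair to say that clustering reduces the false-positive figures, that a bias of 0.1-0.2 points is small beside PHQ-9 bands five scores wide, and that a three-way model with stratum-specific variances would be hard to fit with few centres. The last objection limits the remedy: the fix below avoids that model. What the objection does not answer is that the plan, run as written, neither corrects a gap in mix nor gives an estimate for either tier.

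**Conclusion.** The point holds as a cheap improvement. Two strata are recruited to separate targets by different non-randomised routes, and one arm treats them differently, but the stated analysis contains no stratum adjustment and no stratum estimate. With no gap in mix there is no bias from this source. A gap of 5 or 10 points gives a bias of 0.1 or 0.2 PHQ-9 points, with false positives of about 9% or 22%, falling to about 7% or 14% at a design effect of 2. These sizes rest wholly on the assumed SDs, natural fall, gap and design effect. The loss of interpretation depends on none of them: the pooled result cannot show which tier has an effect.

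**What to change.** **Data Analysis, overall estimate.** State the fixed effects as group, time, group x time, baseline stratum and stratum x time, and keep the Satterthwaite correction.

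**Data Analysis, secondary.** Prespecify the T0-T2 group difference with 95% CI in each stratum, from separate models by stratum so that each has its own variance. Also report the difference between the two stratum effects. Label these results secondary, without multiplicity control. With two strata and two scales, four tests at .05 carry up to 1 - 0.95^4 = about 19% chance of a false positive if independent.

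**Participants.** The targets refer to clinically significant symptoms, while the inclusion criterion starts at mild level. Measurements labels PHQ-9 5-9 as mild, and Interventions divides people with symptoms into mild and moderate. Reconcile these so that each person's stratum is fixed from T0 data. If T0 PHQ-9 defines the stratum, T0 scores are truncated within strata, so model fit should be checked.

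**Cost.** Wording only. PHQ-9 is already collected at T0, and Assessment Procedures already gives the two groups different assessment lengths. The downsides are an imprecise symptomatic contrast and a still less precise difference between strata (step 4). Stratum adjustment does not remove other differences between the non-randomised arms.

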### Measurements

1. Basic demographics: age, gender, marital status, education (years and highest attainment), and work experience.
2. Risk flowchart: a customized questionnaire for quick screening of the following known risk factors for late-life depression: recent spousal death; widowed; disability; living alone; pain & sleep complaints.
3. The Patient Health Questionnaire (PHQ-9) (Kroenke, Spitzer, & Williams, 2001): a 9-item instrument that incorporates depression diagnostic criteria with other leading major depressive symptoms, and rates the frequency of the symptoms which factors into the scoring severity index. PHQ-9 scores of 5-9, 10-14, 15-19, 20 and above represent mild, moderate, moderately severe, and severe depression.
4. Self-harm risk assessment: assessment by social service staff on participant’s risk of self-harm (yes or no answers to 10 items) and harm to others (yes or no answers to 4 items), and in the end social service staff will give an overall evaluation of suicidal risk score ranging from 0-No to 3-High.

5. Generalized Anxiety Disorder scale (GAD-7; Spitzer, Kroenke, Williams, & Lowe, 2006): a 7-item scale, responses to each item are rated on a 4-point Likert scale and range from 0 to 3. The following guidelines are recommended for the interpretation: 5-9 for mild anxiety, 10-14 for moderate anxiety, and 15-21 for severe anxiety.
6. Hong Kong Montreal Cognitive Assessment 5-Minute Protocol (HK-MoCA 5-Min) (Wong et al., 2015): a validated and reliable cognitive screen for stroke and transient ischemic attack, brief and highly feasible for telephone administration. It includes four items examining attention, verbal learning and memory, executive functions/language, and orientation extracted from the MoCA.
7. Name generator: asking participants to list out names of people who they would turn to when they feel down, and when they need help for trivial things.
8. UCLA loneliness scale (UCLA-3) (Hughes, Waite, Hawkley, & Cacioppo, 2004): a 3-item self-report measuring individual's perceived loneliness. Each item is evaluated with scores ranging from 0 (never) to 3 (often), total score is the sum of all items, and higher score indicates higher level of perceived loneliness.

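### The place of people scoring 15 or more on the PHQ-9 is unstated, and the analysis of two non-randomised groups has no stated adjustment for baseline severity

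*Combined protocol and SAP*

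**What the plan says.** Four sections of the combined protocol and SAP bear on this.

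- **Participants.** A person may enter on a risk factor ("have one or more known risk factor(s) for developing depression; and/or") or on symptoms ("have depressive symptoms of mild level or above"). No upper symptom limit is given. The nearest exclusion to a severity limit is "temporary exclusion criteria) imminent suicidal risk", which is temporary and is not a PHQ-9 ceiling. One set of criteria covers both groups. Planned numbers are 1,600 at-risk and 400 symptomatic in the intervention group, and 400 and 100 in the control group. Intervention participants come through the NGOs that deliver the programme; controls come by referral from different NGOs and by open recruitment.
- **Measurements, item 3.** "PHQ-9 scores of 5-9, 10-14, 15-19, 20 and above represent mild, moderate, moderately severe, and severe depression".
- **Interventions.** Care is stepped "according to level of risks, symptom severity, and intervention response". There is a step for at-risk people, and then: "For people with depressive symptoms, we further divide them to “mild” and “moderate” groups". Neither label is tied to a PHQ-9 score. For controls: "The control group will receive treatment as usual, which will be determined by the responsible worker from NGO units".
- **Data Analysis.** Baseline variables are compared between groups by significance tests. Changes in PHQ-9 are assessed by a three-level linear mixed model over two or three time points. No covariate, matching, weighting or stratification for baseline severity is mentioned. The Design section calls the study quasi-experimental.

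**The concern.** If the labels in Interventions carry the PHQ-9 meaning given in Measurements, moderate ends at 14, and a person scoring 15 or more is eligible without a named group. If they do not, the boundary of the upper group is undefined. Either way, a reader cannot tell whether the result for objective 2 (reducing symptoms) covers people in the top two bands.

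This matters more here than in a randomised trial. The severity mix may differ between the groups simply because they are recruited differently, and the plan does nothing to balance severity within the symptomatic stratum. High scorers have more room to fall. If the mix differs and change depends on severity, part of any between-group difference in PHQ-9 change reflects who was enrolled and not what was delivered.

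**Working it through.** **1. The text, side by side.** The plan gives no figure to reproduce, so the first check is of wording.

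| PHQ-9 band (Measurements) | Eligible on symptoms (Participants) | Named group (Interventions) |
|---|---|---|
| 5-9, mild | yes | mild |
| 10-14, moderate | yes | moderate |
| 15-19, moderately severe | yes | not stated |
| 20 and above, severe | yes, unless imminent suicidal risk temporarily excludes | not stated |

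No other section fills the last two cells. The clinically significant symptoms that define the 400 and 100 are not tied to these bands either.

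**2. What the planned numbers balance.** Symptomatic share: 400 / 2,000 = 0.20 and 100 / 500 = 0.20. The strata are in the ratio 4:1 in both cases. At-risk against symptomatic is balanced by plan; severity within the symptomatic stratum is not.

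**3. Scale of a baseline difference (illustration).** All inputs are assumptions: 10-20% of symptomatic controls score 15 or more, no intervention participant does, and mean PHQ-9 is 17.5 in high scorers and 9 in the rest.

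- Shift in the symptomatic stratum = share x (17.5 - 9) = share x 8.5.
- 0.10 x 8.5 = 0.85; 0.15 x 8.5 = 1.28; 0.20 x 8.5 = 1.70 points.
- Strata pooled: 0.20 x 0.85 = 0.17 and 0.20 x 1.70 = 0.34 points.

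This is the full-exclusion case. A partial imbalance gives less: 10% against 5% gives 0.05 x 8.5 = 0.43 points in the stratum.

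**4. From baseline difference to bias.** A baseline shift does not by itself bias a comparison of change. Suppose there is no programme effect, high scorers fall by H points and others by L in both groups, and the shares of high scorers are pC (control) and pI (intervention). Then the spurious difference in mean change is (pC - pI) x (H - L). For a share difference of 0.10 to 0.20 this is 0.10 to 0.20 points in the symptomatic stratum for each extra point that high scorers fall. The documents give neither the shares nor H - L, and the sign follows whichever group has more high scorers.

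**5. Would the planned baseline tests reveal it?** Two-sided 0.05 test of the share scoring 15 or more, 100 controls against 400 intervention participants:

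| Control | Intervention | Power |
|---|---|---|
| 10% | 0% | 0.99 |
| 20% | 10% | 0.75 |
| 10% | 5% | 0.47 |
| 5% | 2% | 0.42 |
| 20% | 15% | 0.24 |

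The extreme case would show; moderate ones could be missed. The plan also does not say what would follow from a significant baseline test.

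**6. Which adjustment has an effect.** The plan's wording implies that T0 PHQ-9 is one of the response rows. Let g be group, t time (0 or 1) and h baseline band. With a main effect only, y = a + b g + c t + d g t + e h, and a person's change is c + d g: the term e h cancels, so with complete two-time-point data d is the same with or without it. With a further term f h t, the change is c + d g + f h, and d is then compared within band. A simulation agreed: the group-by-time estimate was 0.736 without the band main effect and 0.736 with it, but 0.156 with a band-by-time term. Those values depend on the simulated inputs and say nothing about this trial's likely bias.

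**The case against.** The strongest reply is that no person is actually left without a place. Interventions uses mild and moderate as programme labels, gives no cut-offs, and divides everyone with symptoms between them, so moderate may simply mean moderate or above. This stands as a possible reading. It turns a missing step into an undefined boundary, but the text does not confirm it.

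A reader might go further and infer that the intervention NGOs redirect high scorers while control recruitment keeps them. The documents do not support that. No section mentions redirection, one set of entry criteria with no ceiling covers both groups, the suicidal-risk exclusion applies to both, and NGOs take part in control recruitment and care as well. Unequal entry is possible, not documented.

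It is also fair to say that the 0.85-1.70 point shift is an assumed worst case, that it shrinks to 0.17-0.34 when strata are pooled, and that the planned tests would expose it: 0 of 400 against 10 of 100 gives a Fisher exact p of about 7 x 10^-8. Partial imbalances, however, could pass unnoticed.

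Lastly, severity is only one confounder in a non-randomised comparison. That is true, and adjusting for it does not settle the others. It is still the baseline value of the outcome itself, and it is already collected at T0.

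**Conclusion.** The point holds in two limited parts. First, Participants, Interventions and Measurements do not fit together: entry has no upper limit, two PHQ-9 bands lie above moderate, and neither of them has a stated place. This rests on the text alone. Second, with non-randomised groups, different recruitment routes and no stated adjustment for baseline severity, change that depends on severity could bias the PHQ-9 comparison.

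The size and direction of that bias cannot be obtained from the documents. The figures of 0.85-1.70 points (symptomatic stratum) and 0.17-0.34 (pooled) are baseline differences, not bias in change. They rest on an assumed share, assumed means and an all-or-nothing split, and should be read as an upper illustration. The case for changing the analysis does not depend on them: the safeguard is worth having whatever the imbalance proves to be.

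**What to change.** - **Protocol text.** Reconcile Participants, Interventions and Measurements so that every eligible PHQ-9 band has a stated place, and say how the clinically significant stratum relates to the bands. Which clinical rule applies is for the sponsor and investigators; none is proposed here.
- **Data Analysis.** Pre-specify adjustment for T0 PHQ-9 in a form that acts on the group-by-time estimate: either a baseline-band-by-time term, or a model of follow-up PHQ-9 given T0 PHQ-9. Controls are assessed only at T0 and T2, so the between-group contrast is at T2. A band main effect alone is not enough.
- **Reporting.** Give PHQ-9 band counts at T0 by group, within the at-risk and symptomatic strata, whatever the baseline tests show.
- **Sensitivity analysis.** Restricting the comparison to bands enrolled in both groups makes the analysis set depend on observed enrolment. It should not be the main comparison; use it at most as a pre-specified sensitivity analysis.

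The cost is a protocol clarification, a sentence or two in Data Analysis and a little more analysis work. No new data are needed. The adjustment does not remove other confounding from the recruitment routes, and because PHQ-9 is measured with error, some confounding by severity may also remain.
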